7.4.1.2.4 Action and Outcome

• Action taken with study medication (none, study medication stopped, study medication temporarily interrupted)

Verona Pharma plc CONFIDENTIAL Page 42 of 66

- Other actions (none, concomitant medication, study discontinuation, hospitalization, other)
- The outcome and date of outcome according to the following definitions:
 - Recovered or resolved (adverse event disappeared)
 - Recovering or resolving (patient is recovering)
 - Not recovered or not resolved (adverse event remains without signs of improvement)
 - Recovered or resolved with sequelae (adverse event has resulted in permanent disability or incapacity)
 - Fatal
 - Unknown (only applicable if patient has been lost to follow-up)
- Seriousness (yes or no)

7.4.1.3 Reporting Procedure for SAEs

The Investigator must report all SAEs to the Sponsor as soon as practical, but in call cases within 24 hours of awareness. Any fatal SAEs notified in the 28-day period after the last dose of study drug must also be reported

SUSARs will be determined by the Sponsor's Medical Monitor.

SAEs will be reported to the ethics committee(s)/institutional review board(s) and regulatory authority(is) according to local requirements.

All adverse events will be followed until they have abated, or until a stable situation has been reached. Depending on the event, follow up may require additional tests or medical procedures as indicated, and/or referral to the patient's general physician or a medical specialist.

It is the responsibility of the Investigator to ensure that any necessary additional therapeutic measures and follow-up procedures are performed.

7.4.2 Pregnancy

All female patients of childbearing potential will have a serum pregnancy test at Screening. Samples will be taken and handled according to the laboratory manual and analyzed at an approved central laboratory.

Urine pregnancy tests will also be performed by the study center at Screening (confirmed to be negative prior to the chest X-ray), on Day 1 of each treatment period and at the end of study visit.

Should a female patient become pregnant, or if a male patient fathers a child during the study or in the 30 days after the end of the study, the Investigator must be informed immediately. The Investigator will report this information to the Sponsor within 7 days of awareness. The Investigator will make all reasonable efforts to ascertain the progress and outcome of the pregnancy. If the outcome meets the criteria for immediate classification of a SAE (e.g. spontaneous or therapeutic abortion, stillbirth, neonatal death, congenital anomaly, birth defect), the Investigator must follow the procedure for reporting SAEs.

7.4.3 Laboratory Safety Assessments

In addition to the laboratory tests detailed in Section 7.4.3.1 to Section 7.4.3.3, unscheduled and/or repeat testing may be performed at the discretion of the Investigator. Any additional laboratory results will also be merged into the final database. Laboratory results will be

Verona Pharma plc CONFIDENTIAL Page 43 of 66

provided to the Investigator for each patient and each visit. The Investigator should assign whether each abnormal result is not clinically significant or a clinically significant by manually annotating a print out of the results.

Samples will be taken and handled according to the laboratory manual and analyzed at an approved central laboratory.

7.4.3.1 Hematology

The following will be measured at Screening, on Day 4 of each treatment period and at the end of study visit: Hemoglobin, hematocrit, total white cell count, leukocyte differential count and platelet count.

At each timepoint, a sample of venous blood will be collected in a collection tube containing ethylenediaminetetraacetic acid (EDTA).

7.4.3.2 Biochemistry

The following will be measured at Screening, on Day 4 of each treatment period and at the end of study visit: creatinine, total bilirubin, alkaline phosphatase, aspartate aminotransferase, alanine transaminase, gamma-GT, lactate dehydrogenase, creatine kinase, thyroid stimulating hormone, triiodothyronine and thyroxine, glucose, potassium, sodium and calcium. Additionally, follicle-stimulating hormone (FSH) will be measured at Screening, where appropriate, to confirm post-menopausal status.

At each timepoint, a sample of venous blood will be collected in a vacutainer collection tube.

7.4.3.3 *Urinalysis*

A midstream urine sample will be collected in a sterile container at Screening and at the end of study visit. The following will be tested: leucocytes, blood, ketones, bilirubin, urobilinogen, protein and glucose.

If urinalysis on Dipstick is positive for leucocytes and/or blood/hemoglobin, a microscopic examination including erythrocytes, leucocytes, bacteria, casts, epithelial cells and crystals will be performed.

7.4.4 Vital Signs

Blood pressure and pulse rate will be measured at Screening, the end of study visit and the following time points in each treatment period:

- Day 1: pre-dose; 30 minutes and 1, 2, 4, 6, 8 and 12 hours post-dose
- Day 2: pre-dose; 30 minutes and 1, 2, 3, 4 and 12 hours post-dose
- Day 3; pre-dose; 30 minutes and 1, 2, 4, 6, 8 and 24 hours post-dose

Post-dose measurements will be taken in relation to the morning dose of tiotropium/olodaterol and RPL554 or placebo. The 12-hour measurement will therefore be taken pre-dose before the evening dose of RPL554 or placebo. The 24-hour measurement on Day 3 will be taken in the morning on Day 4 prior to discharge from the study center.

At each timepoint, supine vital signs will be assessed whilst the patient has been at rest for at least 5 minutes.

Verona Pharma plc CONFIDENTIAL Page 44 of 66

7.4.5 Physical Examination

A full physical examination, covering major body systems (assessments of the nose, throat, skin, thyroid gland, neurological system, respiratory system, cardiovascular system, abdomen [liver and spleen], lymph nodes and extremities) will be performed at Screening. Results will be recorded in the eCRF as normal, abnormal not clinically significant or abnormal clinically significant and abnormal results described. The full physical examination will be repeated at the end of study visit, and any changes only recorded.

A brief physical examination, including assessments of the skin, respiratory system, cardiovascular system, and abdomen (liver and spleen). will be performed pre-dose on Day 1 and prior to discharge from the study center on Day 4.

7.4.6 12-Lead ECG

12-lead ECGs will be performed at Screening, the end of study visit and the following time points in each treatment period:

- Day 1: pre-dose and 2 and 4 hours post-dose
- Day 2: pre-dose and 2 hours post-dose
- Day 3: pre-dose and 2 and 24 hours post-morning dose

Post-dose measurements will be taken in relation to the morning dose of tiotropium/olodaterol and RPL554 or placebo. The 24-hour measurement at the end of each treatment period will be taken in the morning on Day 4 prior to discharge from the study center.

Each 12-lead ECG should be taken after at least 5 minutes in the supine position. An overall assessment (normal, abnormal not clinically significant or abnormal clinically significant) will be recorded in the eCRF by the Investigator.

Each 12-lead ECG recording will be sent to a central vendor for interpretation.

7.4.7 Holter Monitoring

12-lead Holter monitors will be used to perform 24-hour Holter monitoring. A Holter monitor will be placed at Screening. Monitoring will be ambulatory and will be recorded as an outpatient and the monitor will be removed at the study center after 24 hours. The Screening Holter report must have a minimum of 18 hours recording that is evaluable for rhythm analysis and the report must be reviewed to assess Inclusion criteria prior to Randomization.

A Holter monitor will also be placed at least 30 minutes pre-dose on Day 3 of each treatment period and removed on Day 4.

Holter readings will be sent to a central vendor for interpretation.

Verona Pharma plc CONFIDENTIAL Page 45 of 66

8 QUALITY ASSURANCE AND QUALITY CONTROL

The study will be conducted in accordance with the current approved protocol, standard operating procedures (SOPs) and all applicable guidelines and requirements (see Section 10).

8.1 Audit and Inspection

The Sponsor, or its designee may conduct a quality assurance audit. An inspection of this study may also be carried out by regulatory authorities at their discretion. Such audits or inspections can occur at any time during or after completion of the study. If an audit or inspection occurs, the Investigator and institution agree to allow the auditor/inspector direct access to all relevant documents and to allocate his time and the time of his staff to the auditor or inspector to discuss findings and any relevant issues.

8.2 Monitoring and Source Document Verification

The study will be monitored by a monitor approved by the Sponsor. During these visits, all procedures will be monitored for compliance with the protocol. Source documents will be reviewed and compared with the data entries in the eCRFs to ensure consistency. The Sponsor will ensure that the study is monitored in accordance with the principles of ICH GCP. The frequency of monitoring visits will be determined, in part, by the rate of patient recruitment.

The following are examples of items that will be reviewed at these visits:

- Compliance with the protocol
- Consent procedure
- Source documents
- Adverse event procedures
- Storage and accountability of materials

The monitoring visits also provide the Sponsor with the opportunity to ensure that timely patient accrual and the other Investigator's obligations and all applicable requirements are being fulfilled.

The Investigator must permit the study monitor, the ethics committee, the Sponsor's auditors and representatives from regulatory authorities direct access to all source documents for confirmation of the accuracy and reliability of data contained within the eCRFs (source document verification). Patient confidentiality will be protected at all times.

Source documents are defined as the results of original observations and activities of a clinical investigation, including medical notes. All source documents produced in this study will be maintained by the Investigator and made available for inspection. The original signed informed consent form for each patient will be retained by the Investigator and the second signed original given to the patient.

Source data include, but is not limited to, the following and will be identified in a source data location log:

- Screening/enrolment log
- Medical notes which should be updated after each visit to include visit dates, medical
 history, diagnosis of COPD, concomitant medication, any clinically relevant findings of
 clinical examinations or clinically relevant adverse events/medication changes, SAEs and
 information on patient withdrawal

Verona Pharma plc CONFIDENTIAL Page 46 of 66

- Informed consent form
- 12-lead ECGs
- Laboratory reports
- Visit dates
- Study medication accountability/inventory forms

The study monitor will carry out source document verification at regular intervals. This is an essential element of quality control, as it allows the rectification of transcription errors and omissions.

8.3 Data Management and Coding

Data for each patient will be recorded in an eCRF. Data collection must be completed for each patient who signs an informed consent form and receives at least one dose of study medication.

eCRFs will be designed and produced by the Sponsor or designee and should be completed in accordance with instructions. The Investigator is responsible for maintaining adequate and accurate medical records from which accurate information will be transcribed directly into the eCRFs using a secure internet connection. The eCRFs should be filled out completely by the Investigator or designee as stated on the delegation of responsibilities form. The eCRF system will be Food and Drug Administration Code of Federal Regulations 21 Part 11 compliant.

The eCRFs must be reviewed, signed and dated by the Investigator.

Data entered into the eCRF will be validated as defined in the data validation plan. Validation includes, but is not limited to, validity checks (e.g. range checks), consistency checks and customized checks (logical checks between variables to ensure that study data are accurately reported) for eCRF data and external data. A majority of edit checks will be triggered during data entry and will therefore facilitate efficient 'point of entry' data cleaning.

Data management personnel will perform both manual eCRF review and review of additional electronic edit checks to ensure that the data are complete, consistent and reasonable. The electronic edit checks will run continually throughout the course of the study and the issues will be reviewed manually online to determine what action needs to be taken.

Manual queries may be added to the system by clinical data management or study monitor. Clinical data managers and study monitors are able to remotely and proactively monitor the patient eCRFs to improve data quality.

External data (laboratory safety, Holter, 12-lead ECG and pharmacokinetic data) will be transferred electronically into the study database. Discrepancies will be queried to the site and/or the laboratory until the electronic data and the database are reconciled.

All updates to queried data will be made by authorized study center personnel only and all modifications to the database will be recorded in an audit trail. Once all the queries have been resolved, eCRFs will be locked by password protection. Any changes to locked eCRFs will be approved by the Investigator.

Once the full set of eCRFs have been completed and locked, the Sponsor will authorize database lock and all electronic data will be sent to the designated statistician for analysis. Subsequent changes to the database will then only be made only by written agreement of the Sponsor.

Adverse events will be coded from the verbatim description (Investigator term) using the Medical Dictionary for Regulatory Activities (MedDRA) ([specify version] or later). Prior and

Verona Pharma plc CONFIDENTIAL Page 47 of 66

concomitant medications will be coded according to the World Health Organisation drug code. An independent coding review will be performed by the Sponsor.

The clinical database (in Statistical Analysis System [SAS] format) will be transferred to the Sponsor at the end of the study.

Verona Pharma plc CONFIDENTIAL Page 48 of 66

9 STATISTICAL METHODS

9.1 Statistical and Analytical Plans

This section presents a summary of the planned statistical analyses. A detailed plan describing the analyses to be conducted will be defined before the first patient is enrolled and will include the determination of rules for major and minor protocol deviations. Any deviation from the analysis specified in the protocol or the statistical analysis plan will be detailed and justified in the clinical study report.

9.2 Populations to be Analyzed

Allocation of patients to the analysis populations (and whether any patients or specific data from a patient will be excluded) will be determined at the pre-database lock meeting.

The full analysis set will consist of all randomized patients with sufficient data collected after intake of study treatment to compute the pharmacodynamic parameters on at least two treatment periods. A completer analysis set will consist of all randomized patients that complete all treatment periods.

The safety set will consist of all randomized patients who took at least one dose of study treatment during at least one visit.

The pharmacokinetic data set will consist of all randomized patients with blood sampling performed after at least one dose of RPL544 and with data sufficient to calculate pharmacokinetic parameters.

9.3 Study Endpoints

9.3.1 Primary Endpoint

The primary endpoint is peak FEV₁ (measured in first 4 hours after morning dosing). This will be measured after dosing on Day 3.

The primary comparisons are RPL554 6mg + tiotropium/olodaterol vs RPL554 placebo + tiotropium/olodaterol, followed by RPL554 1.5 mg + tiotropium/olodaterol vs RPL554 placebo + tiotropium/olodaterol.

9.3.2 Secondary Endpoints

- Change from baseline in trough FEV₁ on Day 4 (mean of -1 and 0 time prior to dosing)
- Determination of AUC_{0-4h} FEV₁ after morning dosing on Day 3
- Peak FEV₁ (measured in first 4 hours after dosing) and AUC_{0-12h} FEV₁. These will be measured after dosing on Day 1
- Change from baseline in AUC_{0-12h} FEV₁ measured on Day 3
- Change from pre-evening dose FEV₁ on Day 3 (peak over 4 hours)
- Determination of onset of action (>10% increase in FEV₁, from pre-first dose, censored at 120 minutes) on Day 1
- RV, FRC and sG_{aw} at 1.25 hours on Day 1 and 1.25, 8.25 and 12.25 hours after dosing on Day 3
- RPL554 steady state pharmacokinetics (AUC, C_{max} , time to maximum concentration [t_{max}])

Verona Pharma plc CONFIDENTIAL Page 49 of 66

- Safety and tolerability:
 - Continuous monitoring of adverse events
 - Laboratory safety tests [hematology, biochemistry and urinalysis]
 - 12-lead ECG (including QTcF and heart rate), supine vital signs [blood pressure and pulse rate]
 - Peak (measured in first 4 hours after dosing) and AUC_{0-4h} pulse rate for each treatment period.
 - Holter monitor results

9.3.3 Exploratory Endpoints

- AUC_{0-24h} FEV₁ on Day 3
- Change from baseline in Likert dyspnea scale

9.4 Statistical Methods

In general, unless stated otherwise, continuous variables will be summarized using descriptive statistics (number of patients, mean, standard deviation, median, minimum and maximum values) and for categorical (nominal) variables, the number and percentage of patients will be used.

All hypothesis testing will be done using two-sided alternative hypotheses. P-values less than 5% will be considered statistically significant.

9.4.1 Patient Disposition

The number of patients enrolled, randomized, completed or withdrawn (with reason for withdrawal) will be summarized.

9.4.2 Protocol Deviations

All protocol deviations collected will be divided into critical, major or minor categories. Prior to database lock protocol deviations will be reviewed and consequences for inclusion of patients in various analysis population sets determined and documented.

9.4.3 Demographics and Other Baseline Characteristics

Demographics and baseline characteristics (including pre- and post-bronchodilator FEV₁ [both in liters and in percentage of predicted normal], post-bronchodilator FEV₁/FVC, FEV₁ reversibility, duration of COPD [time since diagnosis], smoking habits including number of pack years, number of patients taking COPD medications by therapeutic class) will be listed and summarized appropriately.

Medical history, prior and concomitant medications, viral serology results, alcohol breath test results, pregnancy test results from females and chest X-ray findings will be listed.

9.4.4 Extent of Exposure and Treatment Compliance

All administration of study treatment will be done at the clinic under supervision of the study staff; therefore, no formal analysis of compliance will be performed. The RPL554 exposure will be estimated based on residual volume in the nebulizer cup.

Verona Pharma plc CONFIDENTIAL Page 50 of 66

9.4.5 Efficacy/Pharmacodynamics

FEV₁ and FVC will be summarized as actual and change from baseline using descriptive statistics over time.

The peak effect on FEV_1 during these time intervals will be computed as the maximum value in the 4 hours after dosing. The average effect will be calculated as the AUC divided by the length of the time interval of interest. For analysis, the peak, average and trough FEV_1 will be divided by the pre-dose Day 1 baseline value.

Computed pharmacodynamic parameters for FEV_1 will be compared between the three study treatments using analysis of covariance (ANCOVA) models with fixed factors for treatment, period and patient, and using the pre-dose Day 1 baseline value as a covariate. FEV_1 will be analyzed using multiplicative models, which means that data (dependent and baseline) are logged prior to analysis and the result then transformed back to the linear scale giving treatment differences as ratios of geometric means.

Primarily the combination RPL554+tiotropium/olodaterol will be compared to tiotropium/olodaterol alone for each of the two doses of RPL554. Results of the comparisons will be expressed as the mean geometric ratio with 95% confidence intervals and associated, 2-sided, p-value.

Onset of action will be summarized by treatment and a Kaplan-Meier plot illustrating time to onset constructed.

Outcomes from the whole body plethysmography at 1.25 hours post-dose on Day 1 and 1.25, 8.25 and 12.25 hours post-dose on Day 3 will be compared in the same way as FEV₁ using multiplicative ANOVA models. The baseline of the visit (pre-first dose in a treatment period) will be used as covariate in these models.

The use of rescue medication during the study visits will be summarized by treatment, and, if appropriate, a Kaplan-Meier plot illustrating time to first use of rescue constructed.

9.4.6 Pharmacokinetics

The following steady state pharmacokinetic parameters will be calculated from plasma concentrations of RPL554 using standard non-compartmental methods.

- AUC_{0-12h} represents the area under the plasma concentration curve from time 0 to 12 hours after dose on Day 3. The AUC_{0-12h} value in indicative of the steady state AUC_T for a twice daily dosage regimen of RPL554 for the study cohort
- C_{max} denotes the highest plasma concentration measured
- t_{max} denotes the time point corresponding to C_{max}

Pharmacokinetic parameters will be summarized by dose level using descriptive statistics (n, geometric mean, coefficient of variation (CV), minimum, maximum and median for AUC parameters, C_{max} , n, arithmetic mean, standard deviation, minimum, maximum and median for t_{max}).

9.4.7 Safety

Safety data including safety laboratory tests, 12-lead ECG and Holter parameters, vital signs and physical examinations, will be summarized by treatment group and time point of collection, when appropriate. For continuous variables, the change from baseline (pre-dose at each treatment period) to each post-dose time point will also be calculated and summarized. Data will further be illustrated by shift tables (showing changes from low/normal/high) and shift

Verona Pharma plc CONFIDENTIAL Page 51 of 66

plots for selected time points. Separate listings will be generated of abnormal values occurring after the first dose of study treatment.

Coded adverse event terms will be presented by system organ class (SOC) and preferred term and summarized by treatment group. A summary table by treatment group with total number and number of patients with adverse events, SAEs, adverse events leading to discontinuation of study treatment, causally related adverse events and severe adverse events will be produced. Further, SAEs, causally related adverse events and adverse event of each intensity will be summarized by SOC and preferred term.

9.4.8 Handling of Withdrawals or Missing Data

Patients withdrawn after only one treatment period will not be included in the efficacy analyses. Imputation of data for calculation of average (AUC) effects for FEV₁ will be described in the statistical analysis plan. No other imputation of missing data will be performed.

All available data from all dosed patients who have received study treatment will be listed and summarized. Any unscheduled or unplanned readings will be presented within the patient listings, but only the scheduled readings will be used in any summaries. If a visit is rescheduled due to variability in FEV₁ or other reason, the rescheduled visit will be listed and summarized as the valid visit.

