4.3.2 Patient Withdrawal

Investigators have the authority to withdraw a patient at any time for medical or non-compliance reasons. Should the Investigator decide it is necessary to withdraw any patient for specific reasons, this should be recorded in writing and transmitted to the patient in question. Such reasons for withdrawal are expected to be medical or related to lack of co-operation by the patient.

The patient has the right to withdraw at any time and for any reason, without explanation and without jeopardizing any subsequent treatment by the clinician, if applicable. However, anyone withdrawing should be encouraged to offer an explanation for their withdrawal, particularly if it relates or is perceived to relate in any way to the study treatment, or to the conduct of the study. Patients can also be withdrawn in case of protocol violations and non-compliance.

If a patient withdraws following Randomization, every attempt should be made to contact the patient to determine the reason for withdrawal and to complete the recording of any available efficacy data and all adverse event data. The reasons for withdrawal and results of all relevant

Verona Pharma plc CONFIDENTIAL Page 22 of 66

tests will be recorded in the electronic case report form (eCRF). These patients should have an end of study visit unless it is considered by the Investigator that they require greater medical supervision and/or investigations and in which case an unscheduled visit prior to and in addition to the scheduled follow up visit may be performed.

If a patient had signed a consent form but withdrew from the study without receiving any study treatment, no further follow-up is necessary.

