6.3. REPEAT/RESCHEDULE, UNSCHEDULED VISITS AND EARLY TERMINATION DATA

In general, for by-visit summaries, data recorded at the nominal visit will be presented. If a visit is repeated/rescheduled due to variability in FEV₁ or other reason, the repeated/rescheduled visit, will be listed and summarized as the valid visit (same visit number assigned), at the discretion of the Investigator. Unscheduled measurements will not be included in by-visit summaries, but will contribute to the endpoint value, at the discretion of the Investigator. For example, if an unscheduled visit occurred at 10 hours post-dose on Day 3, then this value will be considered in the calculation of the average FEV₁ over 12 hours (AUC_{0-12h} FEV₁) on Day 3. Any unscheduled or unplanned readings will be presented within the patient listings.

Early termination data will be mapped according to the visit number the termination occurred for by-visit summaries. If early termination occurs pre-first dose (after baseline), then it is summarized at the actual visit. If

Document: Z:\RPL554\UYA25849\Biostatistics\Documentation\SAP\Verona RPL554-CO-204 SAP v1.0

Author: [name] Version Number: 1.0

Version Date: [18OCT2018]

Template No.: CS_TP_BS016 Revision 5 Reference: CS_WI_BS005

Effective Date: 01Apr2018

Page 17 of 50

termination is after first dose in period or during the following wash-out period, data collected remains at the visit performed. However, if the patient returns for end of study, then this data will be mapped to end of study visit.

If AE data occurs in the 7 to 14-day gap between treatment periods, these will be mapped to the earlier of the two treatment periods. Similarly, the AE will be mapped to the last treatment group received. If AE data occurs in the post-treatment period, these will be mapped to the last treatment period and last treatment group received.

Listings will include scheduled, unscheduled, repeat/reschedule and early discontinuation data.

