16.2. LABORATORY EVALUATIONS

Results from the central laboratory will be included in the reporting of this study for hematology, blood chemistry and urinalysis. A list of laboratory assessments to be included in the outputs is included in the protocol, Sections 7.4.3.1, 7.4.3.2 and 7.4.3.3 for hematology, blood chemistry and urinalysis, respectively. Presentations will use SI Units.

Quantitative laboratory measurements reported as "< X", i.e. below the lower limit of quantification (BLQ), or "> X", i.e. above the upper limit of quantification (ULQ), will be converted to X for quantitative summaries, but will be presented as recorded, i.e. as "< X" or "> X" in the listings.

The following summaries will be provided for laboratory data:

- Actual and change from baseline (pre-dose at each treatment period) to each post-dose time point (for
 quantitative measurements), including overall (where overall is regardless of treatment period, day and
 timepoint to assess treatment group as a whole).
- Incidence of abnormal values according to normal range criteria
- Shift from baseline according to normal range criteria (for quantitative measurements and categorical

Document: Z:\RPL554\UYA25849\Biostatistics\Documentation\SAP\Verona RPL554-CO-204 SAP v1.0

Author: [name] Version Number: 1.0

Version Date: [18OCT2018]

Template No.: CS_TP_BS016 Revision 5 Reference: CS_WI_BS005

Effective Date: 01Apr2018

Page 38 of 50

measurements)

• Listing of abnormal values occurring after the first dose of study treatment.

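### Protocol 9.4.8 bars unscheduled readings from every summary and SAP 6.3 only from by-visit ones; under the protocol rule, laboratory and ECG abnormality incidence can be understated

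*Protocol*

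**What the plan says.** **Protocol.** Section 9.4.8 places unscheduled readings in the listings and states that "only the scheduled readings will be used in any summaries". The sentence before it reads "All available data from all dosed patients who have received study treatment will be listed and summarized", which pulls the other way.

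The protocol expects such readings to exist. Section 6 allows unscheduled visits and procedures at the Investigator's discretion. Section 7.4.3 allows unscheduled or repeat laboratory tests and adds "Any additional laboratory results will also be merged into the final database". For withdrawn patients who need closer medical supervision, Section 4.3.2 says that "an unscheduled visit prior to and in addition to the scheduled follow up visit may be performed".

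**SAP.** Section 6.3 states: "Unscheduled measurements will not be included in by-visit summaries, but will contribute to the endpoint value, at the discretion of the Investigator". Its one example is an extra FEV1 reading used in an AUC. Section 16.2 plans a table headed "Incidence of abnormal values according to normal range criteria" and a laboratory shift table. Section 16.3 plans an incidence table for markedly abnormal ECGs and an ECG shift from baseline to post-dose time points. Neither section says whether unscheduled values count. Section 3.3 reports no changes from the protocol.

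**The concern.** Using scheduled readings only is sensible for a mean at a given time point, because an extra reading has no natural place there. A table that counts patients who ever had an abnormal value asks a different question. Leaving out a known abnormal result there records the patient as having none.

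Unscheduled tests are often ordered because of symptoms or an abnormal result already seen, so they are unlikely to be a random sample of a patient's values. Safety and tolerability on top of tiotropium/olodaterol is a secondary objective (Protocol 2.2), and these tables are part of how it will be reported. The two documents also give different rules for the same data. The content of a safety table could therefore depend on which rule the programmer follows or, under SAP 6.3, on an Investigator's discretion.

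**Working it through.** The plan states no figure on this point, so there is none to reproduce. The check compares the texts and then sizes the effect.

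**1. Which rule applies to which table**

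- Means and other statistics by time point: Protocol 9.4.8 and SAP 6.3 agree on scheduled readings only.
- Laboratory incidence of abnormal values (SAP 16.2): excluded under Protocol 9.4.8, because the rule covers every summary. Unresolved under SAP 6.3, because the table is not described as by-visit and Section 16.2 is silent.
- ECG incidence of markedly abnormal results (SAP 16.3): as for the laboratory incidence table.
- Laboratory shift (SAP 16.2): excluded under the protocol. Under the SAP it depends on whether the shift is built by time point or on the worst value, which is not stated.
- ECG shift (SAP 16.3): defined by post-dose time point, so scheduled readings only is appropriate.
- Vital signs (SAP 16.4): actual values by time point only, with no incidence or shift table.

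**2. Scheduled readings that could catch the abnormality anyway**

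- Laboratory (Protocol 6.3.3.3, 7.4.3.1, 7.4.3.2): one on-treatment draw per period, on Day 4. That is 24 hours after the Day 3 morning dose and about 12 hours after the last RPL554 or placebo dose. A value nearer to dosing could come only from an unscheduled test.
- ECG (Protocol 7.4.6): Day 1 at 2 and 4 hours, Day 2 at 2 hours, Day 3 at 2 and 24 hours. That is 2 + 1 + 2 = 5 post-dose readings per period.

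**3. Who is missed**

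A patient is missed only if every scheduled post-dose value on that treatment is normal and an unscheduled one is abnormal. If an abnormal scheduled post-dose value prompted the repeat test, the patient is already in the table.

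**4. Size**

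The denominator is taken as the planned 70 patients (Protocol 4.3.4, 9.5). The actual number per treatment may differ.

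- Fall in incidence with m patients missed = m/70. For m = 1, 2, 3, 5: 1.4, 2.9, 4.3, 7.1 percentage points.
- Illustration: 3 affected patients with 1 missed gives 2/70 = 2.9% in place of 3/70 = 4.3%.
- Let q be the proportion of patients on a treatment whose only abnormality is unscheduled. The documents give no value, so q is an assumption. Expected number missed = 70q, and the chance of missing at least one = 1 − (1 − q)^70:
  - q = 0.5%: 0.35 expected, 30%
  - q = 1%: 0.7 expected, 51%
  - q = 2%: 1.4 expected, 76%
  - q = 5%: 3.5 expected, 97%

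**The case against.** The best reply is that the SAP has already put this right. Protocol 9.1 calls Section 9 a summary and leaves the detail to the SAP, and SAP 6.3 restricts the exclusion to by-visit summaries. On that reading the incidence tables may include unscheduled values. This stands in part: it would be wrong to say that the SAP excludes them. But the SAP does not include them either. Its only stated route into an analysis is discretionary and illustrated by an efficacy endpoint, and SAP 3.3 does not claim to depart from the protocol.

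A second reply is that abnormal results are visible elsewhere. Adverse events are recorded throughout (Protocol 7.4.1.2) and tabulated. Abnormal post-dose laboratory values and patients with markedly abnormal ECGs are listed (SAP 16.2, 16.3). The Investigator judges each abnormal laboratory result for clinical significance (Protocol 7.4.3). For this reason, a reader who infers that harm as a whole is undercounted goes further than the documents allow. The safeguard is still partial: nothing in either document requires an abnormal laboratory or ECG value to be recorded as an adverse event, and a listing does not change a tabulated incidence.

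A reader might also extend the point to vital signs. The SAP does not support that, because it plans no incidence or shift table for them; only the general shift-table sentence in Protocol 9.4.7 could reach them.

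Finally, safety is descriptive (SAP 16) and the rule treats all three treatments alike. That is correct, and it limits the claim to each treatment's own incidence.

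**Conclusion.** The point holds in a limited form. The protocol states a rule that, applied as written, can understate the incidence of laboratory and ECG abnormalities on each treatment. The SAP differs from that rule without saying so and leaves those tables undecided.

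The loss is 1.4 percentage points per missed patient at n = 70. The number missed is unknown and may be zero. Laboratory results are the more exposed, with one scheduled on-treatment draw per period against five post-dose ECGs. It would be tempting to conclude that RPL554 will look safer than placebo. The documents do not support this, since the rule covers placebo too and nothing indicates on which treatment extra tests would cluster.

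The comparison with SAP 3.3 rests on one assumption. The SAP names protocol version 2.0 as its basis, while the protocol's amendment page describes itself as a first version. Section 9.4.8 is taken to read the same in both.

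**What to change.** - **Protocol 9.4.8:** limit the scheduled-only rule to descriptive statistics by time point and shifts by time point. This matches SAP 6.3 and removes the tension with the preceding sentence.
- **SAP 16.2 and 16.3:** state that the incidence tables, and any laboratory shift table based on the worst value, count all post-dose readings: scheduled, repeat and unscheduled. Make this a fixed rule, not a matter of Investigator discretion.
- **Assignment to treatment:** give readings in a washout to the earlier treatment and readings after Period 3 to the last treatment, as SAP 6.3 already does for adverse events.
- **SAP 3.3:** record the change.

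The cost is a few sentences and a worst-value flag in programming, with no new data. One drawback is that a treatment under which patients are tested more often can show more abnormalities. Showing the number of patients with at least one unscheduled test, by treatment, beside each incidence table makes that visible.
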